9.6. Method of Assigning Subjects to Treatment Groups

In the double-blind, parallel-group, randomized period of the study, subjects who meet study entry criteria will be randomly assigned in a 1:1:1 ratio to trifarotene cream HE1 100 µg/g or 200 µg/g or vehicle cream. The randomization schedule will be computer generated using a permuted block algorithm and will randomly allocate IP to randomization numbers. The randomization numbers will be assigned sequentially through a central interactive web response system (IWRS) as subjects are entered into the study. Study center will not be a blocking factor in the randomization schedule.

Premier Research will prepare the randomization schedule before the start of the study. No one involved in the study performance will have access to the randomization schedule before the official unblinding of treatment assignments. No subject will be randomized into this study more than once.

In the OLE, all subjects will receive trifarotene cream HE1 200 µg/g.

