At all sites with photographic capability photographs will be taken as source data to support scoring at Baseline, Day 30, and Day 90. A central reader who will not be an investigator in the study will review the photographs to assess consistency of investigator scoring of LI severity as a quality check. Photographs may also be used for scientific publication purposes. Subjects will sign a separate, optional, photographic informed consent form (ICF).

Samples for PK will be drawn from all subjects at Baseline and at each clinic visit, as indicated in the Schedule of Events (Table 2-1). Visits for PK must occur at least 24 hours after the last application of the IP to avoid contamination of the blood samples with any IP that may have remained in the skin after the last application. Subjects should not apply IP on visit days until after the visit.

In addition, a PK substudy will be conducted on Days 1 and 30 at sites with the capability to conduct it. Participation in the PK substudy will be optional and will include at least 15 adults and 15 adolescents. Subjects who participate in the PK substudy will come from both study cohorts and will undergo serial blood sampling predose and at 1, 2, 4, 8, 12, and 24 hours postdose on Day 1 and Day 30. Trough levels will be drawn for all subjects at specified time points. For the subjects in the PK substudy, postdose ECGs will be performed at each serial blood draw on Day 1 and Day 30.

Efficacy will be assessed by the number of subjects in each treatment group who achieve “success” defined as clear/almost clear overall and at least a 50% reduction from Baseline at Week 12/end-of-treatment (EOT) in the Double-blind Period on the 5-point IGA scale (i.e., 0 = clear; 1 = almost clear; 2 = mild; 3 = moderate; 4 = severe). In addition, efficacy criteria include assessment scales for palm/sole, scaling, roughness, fissuring, and the Dermatology Life Quality Index (DLQI), and the EQ-5D Quality of Life (QoL) Questionnaire. Ectropion Severity Scores (ESS) between the active trifarotene cream HE1 and vehicle groups will be an exploratory endpoint.

Plasma concentrations of CD5789 and its major metabolites will be measured.

Safety will be assessed by evaluating reported adverse events (AEs), changes in clinical laboratory test results, vital sign measurements, physical examinations, 12-lead ECGs, and local tolerability.

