13.1.4.2 Primary Analysis

For the Double-blind Period only, the number and proportion of subjects in each treatment group with successful resolution of LI by Week 12/EOT will be presented. The primary efficacy endpoint will be analyzed using a logistic regression model with treatment and age group as factors. Other baseline characteristics and interactions may be included. The odds ratios and 95% CIs for the odds ratios will be presented. The difference in proportions between the active trifarotene cream HE1 and vehicle cream group, 95% CIs for the differences, and P-values for the differences in treatment will also be presented.

Descriptive summaries (such as mean, standard error, median, minimum, and maximum) and the changes from baseline will be provided for IGA scores for both periods.

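### Section 9.6 specifies no stratification by age group, so adolescents, and their serial PK profiles at each dose, are balanced across arms only by chance

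*Protocol*

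**What the plan says.** Section 9.6 says eligible subjects "will be randomly assigned in a 1:1:1 ratio to trifarotene cream HE1 100 µg/g or 200 µg/g or vehicle cream". On method it says: "The randomization schedule will be computer generated using a permuted block algorithm and will randomly allocate IP to randomization numbers", and "The randomization numbers will be assigned sequentially through a central interactive web response system (IWRS) as subjects are entered into the study". The only possible factor it discusses is centre: "Study center will not be a blocking factor in the randomization schedule". Age group is not mentioned and block size is not given.

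Age matters elsewhere in the plan:

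- **Primary model (Section 13.1.4.2):** "The primary efficacy endpoint will be analyzed using a logistic regression model with treatment and age group as factors". Section 13.1.4.5 uses the same two factors for the roughness and palm/sole responder models.
- **PK substudy (Section 7.1):** "Participation in the PK substudy will be optional and will include at least 15 adults and 15 adolescents". Serial sampling is on Days 1 and 30 only.
- **Cohorts (Section 7.1):** Cohort A is about 15 adults. Adolescents enter only in Cohort B, up to about 105 adults and adolescents together, with no adolescent quota.
- **PK summaries (Section 13.1.5.1):** PK parameters are summarised by treatment. No summary by age within treatment is stated.

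**The concern.** Age group is known before randomisation, is prespecified in the primary model and defines a recruitment minimum in the PK substudy, but nothing in the allocation uses it. Permuted blocks balance the whole list. They do not balance a minority scattered through it.

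The part that analysis cannot repair is the adolescent serial PK data. Vehicle subjects supply no exposure profile, so 15 adolescents allocated 1:1:1 already means only about 15/3 = 5 per active dose. If chance gives one dose clearly fewer, the profiles cannot be collected later. Serial sampling stops after Day 30, and in the open-label extension everyone receives 200 µg/g with single PK samples at Weeks 16 and 24. Section 5.2 notes that absorption in lamellar ichthyosis may exceed that in healthy volunteers, which is a reason not to leave adolescent profiles at a dose thin.

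**Working it through.** The protocol gives no figure for adolescent balance, so there is none to reproduce.

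**Inputs.** The allocation is 1:1:1 in permuted blocks (Section 9.6). Cohort B has about 105 subjects (Section 7.1), hence 105/3 = 35 per arm if the blocks complete. PK adolescents are taken as exactly 15, the stated minimum. I assume they fall at random positions among the 105. The cut-off of 3 against an expected 5 is my choice, not the protocol's.

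**Allocation as written.** Let a, b and c be the PK adolescents on 100 µg/g, 200 µg/g and vehicle, with a + b + c = 15. Then

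P(a, b, c) = C(35,a) × C(35,b) × C(35,c) / C(105,15).

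Sum over the relevant cells and combine the two active doses as P(either) = 2 × P(a given dose) − P(both):

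| Event | Given active dose | Both active doses | At least one active dose |
|---|---|---|---|
| 3 or fewer | 0.1893 | 0.0087 | 2 × 0.1893 − 0.0087 = 0.370 |
| 2 or fewer | 0.0642 | 0.0003 | 2 × 0.0642 − 0.0003 = 0.128 |

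Simulating actual permuted blocks over 105 subjects (30,000 runs each) gives 37.0%, 37.0% and 36.9% for 3 or fewer with block sizes 3, 6 and 9. The unstated block size therefore makes no practical difference.

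**Sensitivity to the number of PK adolescents.** The same formula with 18 in place of 15 gives 16% for 3 or fewer on at least one active dose, so the risk falls quickly if the substudy exceeds its minimum.

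**Stratifying by age group only.** Suppose the adolescents who enrol, A in total, are exactly balanced with A/3 per arm, and the 15 in the PK substudy are a random subset of them. Replace 35 by A/3 and 105 by A. The protocol does not give A; the range is assumed.

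| Adolescents enrolled (assumed) | P(3 or fewer on at least one active dose) |
|---|---|
| 15 (all in the substudy) | 0% |
| 21 | 12.8% |
| 30 | 24.4% |
| 42 | 30.2% |

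The residual arises because the substudy is optional: balancing all adolescents does not balance those who agree to serial sampling.

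**Stratifying adolescents also by PK participation.** In a stratum of 15, blocks of 3 give exactly 5/5/5. Blocks of 6 give two full blocks (4 per arm) plus 3 more subjects, so at least 4 per arm. Blocks of 9 give one full block (3 per arm) plus 6 more, so an arm could still end at 3.

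**The case against.** Four points can be made against the concern.

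- **No target is missed.** The exposure objective in Section 6.2 and the PK minimum in Section 7.1 set no adolescent number per dose. A reader might infer that the protocol wants adolescent exposure at each dose. That is a plausible reading of an age-specific minimum combined with by-treatment summaries, but no section states it. This stands.
- **Other adolescent data are unaffected by the substudy.** A reader might infer that adolescent tolerability and all exposure data at a dose could rest on two or three subjects. The documents do not support that. Local tolerability is scored at every clinic visit in all subjects (Sections 9.4 and 13.1.6.1). Single PK samples are drawn from all subjects at Baseline and each double-blind clinic visit (Sections 7.1 and 10.3.2.2). This stands, and it confines the PK point to the serial profiles.
- **The efficacy analysis is sound.** A reader might think that a model factor must also be a stratification factor. It need not be: adjusting for age group deals with chance imbalance in the primary analysis. This stands.
- **Section 9.6 is silent rather than explicit.** It does not say that age is excluded. But allocation factors belong in this section, it raises and dismisses centre, and it describes sequential assignment from a schedule. As specified, there is no age stratum.

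On size, treating the 15 adolescents as independently assigned gives 40.6%. That ignores the permuted blocks the section specifies, so about 37% is the figure to use.

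**Conclusion.** The point holds as a modest design weakness, not as an error or a contradiction. No age stratification is specified, so adolescent numbers by dose are left to chance. With exactly 15 PK adolescents at random among about 105 Cohort B subjects, the chance that at least one active dose has 3 or fewer adolescent serial profiles is about 37%, and about 13% for 2 or fewer. Both figures depend on the assumed 15 and shrink if more adolescents join. What is at stake is the Day 1 and Day 30 adolescent profiles and the balance of adolescents by dose. Neither the validity of the primary efficacy analysis nor compliance with any stated PK target is in question.

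**What to change.** In Section 9.6, stratify the Cohort B schedule by age group (12–17, 18 and over) with small permuted blocks and, within adolescents, also by PK-substudy participation. That makes three strata: adults, adolescents in the substudy, and adolescents not in it. Blocks of 3 or 6 hold each arm to at least 4 of 15 PK adolescents. Keep age group in the primary model.

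This is workable because both factors can be known in time. A signed PK consent is inclusion criterion 6 for those taking part (Section 8.2.1). At the Baseline Visit eligibility is reviewed at step 1 and randomisation is step 16 (Section 10.2.2.1). The protocol should say explicitly that the PK consent is obtained before randomisation.

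The cost is IWRS configuration and a few incomplete blocks. Stratifying by age group without PK participation is a weaker option: it balances adolescents overall but leaves the 0% to about 30% residual risk shown above.

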9.7. Blinding and Unblinding Treatment Assignment

All subjects, investigators, and study personnel involved in the conduct of the Double-blind Period of the study, including data management, will be blinded to treatment assignment with the exception of a specified unblinded statistician and programmer from Premier Research who will have access to the randomization code. The statistician will have access to unblinded data if there is an unblinded DSMB review.

Study personnel will make every effort to safeguard the integrity of the study blind to minimize bias in the conduct of the study. Treatment unblinding is discouraged if knowledge of the treatment assignment will not materially change the planned management of a medical emergency. Unblinding will be permitted in a medical emergency that requires immediate knowledge of the subject's treatment assignment.

The investigator may discuss with the medical monitor in advance of unblinding a subject, if possible, if it is not deemed an emergency. However, the investigator has the ultimate decision for unblinding a subject for medical treatment and no procedures will prevent or delay necessary unblinding in an emergency for the subject's safety. For emergency unblinding, study personnel will use the IWRS code. If the investigator is not able to discuss treatment unblinding in advance, then he/she must notify the medical monitor as soon as possible about the unblinding incident without revealing the subject's treatment assignment.

The investigator or designee must record the date and reason for treatment unblinding on the appropriate eCRF for that subject. In all cases that are not emergencies, the investigator must discuss the event with the medical monitor prior to unblinding the subject's treatment assignment.

If treatment assignment is unblinded for an individual subject, study personnel will be notified of that subject's treatment assignment without unblinding the treatment assignments for the remaining subjects in the study. Thus, the overall study blind will not be compromised. If a subject's treatment assignment is unblinded, he/she may or may not be asked to withdraw from the study. The investigator will make this decision after consultation with the medical monitor.

The primary analysis period is the first 12 weeks of treatment (i.e., the Double-blind Period). Overall unblinding will take place at the end of the Double-blind Period of the study only after database lock has been achieved. A second analysis will take place for endpoints assessed from Week 12 through the OLE.

9.8. Permitted and Prohibited Therapies

All concomitant medications used (including over-the-counter medications and herbal supplements) will be recorded in the source document and on the appropriate eCRF.

Upon signing informed consent and entering the Screening Period, subjects will stop using physical and medical treatments for LI, including balneotherapy, and may begin to washout prohibited topical and systemic treatments with designated washout periods ([Table 9-1](#)), as applicable. Washout may be up to 3 months, as necessary.

Table 9-1: Washout Periods for Prohibited Medications

Medication	Washout Period
Topical Treatments	
Corticosteroids (except inhaled and ophthalmic corticoids)	2 weeks
Retinoids (e.g., tretinoin, tazarotene)	4 weeks
Vitamin D analogues	2 weeks
Immunosuppressants (e.g., tacrolimus)	2 weeks
Antracene derivatives, tar and salicylic preparations	2 weeks
Keratolytics (such as urea, lactic acid, propylene glycol, salicylic acid) except keratolytic shampoo	2 weeks
Systemic treatments	
Retinoids	8 weeks
Oral Vitamin A supplementation more than 3500 IU per day	2 weeks
Medication interfering with bone activity, e.g., corticosteroids, thyroid hormones, cytotoxics, bisphosphonates, calcitonins, tetracyclines, quinolones, thiazides, salicylates in long-term course, heparin, theophylline, barbiturates, colchicines (except Vitamin D analogues taken at stable dose since at least 1 month)	8 weeks
QT prolonging drugs	5 half lives
Enzymatic inductors (such as rifampicine, phenytoin, carbamazepine, phenobarbital, St. John's Wort)	3 months
CYP2C9 and 2C8 inhibitors (not all inclusive: gemfibrozil, fluconazole, fluvoxamine, sulfaphenazole, miconazole, amiodarone, sertraline, sulfamethoxazole, valproic acid, voriconazole, trimethoprim, rosiglitazone, pioglitazone)	5 half lives
Monoclonal antibodies (e.g., anti-IL17)	5 half lives

During washout, subjects may continue taking usual care of visible skin (face and scalp) for cosmetic reasons and of extremities (hands and feet) to avoid functional consequences on walking or moving their fingers. Subjects may shower, but not bathe or swim. The IGA will be evaluated on the rest of the body at Baseline.

After completing any necessary washout of prohibited medications, subjects will return to the site to complete the study eligibility requirements.

9.8.1 Permitted Therapies

Subjects will be advised on permitted emollient(s) for use as often as needed on nontreatment days during the study; on treatment days, the use of emollient(s) is permitted except within 4 hours before or after study drug application. Similarly, protective sunscreen should be applied as often as needed, except within 4 hours before or after study drug application. Subjects may use their standard of care treatment on their faces and/or palms/soles after the Week 4 assessment if they experience a worsening of IGA in those areas. In the US/EU, this may include compounded emollients with keratolytics (alpha or beta hydroxyl acids) and/or urea. These standard of care treatments should be approved by the investigator and documented in the eCRF.

Subjects who enter the OLE must stop standard of care treatment. If they experience a worsening of IGA they may use standard of care treatment on their faces and/or palms/soles after the Week 16

visit if the standard of care does not contain prohibited medications. If those standard of care treatments include prohibited medications, the subject should be discontinued from the study.

Other concomitant medications are allowed (e.g., analgesics, antihistamines), but should be limited to those medications considered necessary. All concomitant medications, both prescribed and over-the-counter, should be recorded in the eCRF.

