9.8.2 Prohibited Therapies

The medications listed in [Table 9-1](#) are prohibited during the study. Balneotherapy is also prohibited during the Screening Period and during the study.

Subjects may not use concomitant keratolytics such as urea, salicylic acid, alpha, or beta hydroxyacids. Subjects may not use topical or systemic retinoids. Subjects may not take more than 3500 IU/day Vitamin A (e.g., as in a multivitamin). Use of benzoyl peroxide is permitted on nontreatment days for subjects with concomitant acne only); it must not be applied on treatment days due to risk of inactivation of trifarotene by benzoyl peroxide.

Subjects receiving excluded therapies will be ineligible for study enrollment or for continued treatment in the study, at the investigator's discretion with consultation with Mayne Pharma LLC and the medical monitor. For enrolled subjects who require prescription of a systemic azole, the principal investigator should discuss with the medical monitor whether the subject may continue in the study.

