10.3.1.1 Investigator’s Global Assessment

The primary endpoint is the number of subjects in each treatment group who experience successful resolution of LI where “success” is defined as clear/almost clear and at least a 2-grade change from Baseline at Week 12/EOT in the Double-blind Period on a 5-point IGA full body scale.

The investigator will rate the subject's condition using the 5-point IGA at each time point shown in the Schedule of Events (Section 2.2).

The IGA will be measured on a 5-point scale, excluding the following areas: knees, elbows, neck, palms, soles, axillae, groin, and scalp:

0	Clear	No scaling and no roughness
1	Almost Clear	Occasional fine scales; hardly palpable roughness (mostly smooth)
2	Mild	Small and fine scales predominate; no more than a few large scales; mild roughness on palpation
3	Moderate	Some large scales that may be thick,; coarse roughness on palpation
4	Severe	Confluent, primarily large (>1 cm), thick scales with plate-like hyperkeratosis

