13.1.4.3 Secondary Analyses

Secondary and exploratory efficacy endpoints will be analyzed separately for each period (Double-blind and OLE) using descriptive statistics.

Additionally, for the Double-blind Period only, change from Baseline in continuous secondary endpoints through Week 12 will be presented and analyzed using a mixed model for repeated measures (MMRM). The model will include the change from baseline score as the dependent variable, treatment group as a fixed effect, subject as a random effect, and baseline score value as a covariate.

For subjects who report having fissures, descriptive summaries of the number of fissures and pain related to fissures will also be presented by treatment group and body area for each period.

The DLQI scores will also be analyzed using descriptive statistics through Week 12.

The proportion of subjects with at least a 50% reduction in IGA score from Baseline will be analyzed using the same logistic regression analysis described in Section [13.1.4.2](#).

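### Palm/sole scores, fissures and the 2-grade palm/sole response at Weeks 8 and 12 can be read under outcome-triggered keratolytic standard of care, with no rule for those readings and conflicting text on whether keratolytics are allowed

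*Protocol*

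**What the plan says.** All references are to the protocol as amended (Amendment 1).

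- **Permission.** Section 9.8.1 says: "Subjects may use their standard of care treatment on their faces and/or palms/soles after the Week 4 assessment", but only "if they experience a worsening of IGA in those areas". On content it says that in the US/EU "this may include compounded emollients with keratolytics (alpha or beta hydroxyl acids) and/or urea". The investigator should approve the treatment, and it should be documented in the eCRF.
- **Prohibition.** Section 9.8.2 says: "Subjects may not use concomitant keratolytics such as urea, salicylic acid, alpha, or beta hydroxyacids". It states no exception for the face, palms or soles after Week 4. Table 9-1, whose medications Section 9.8.2 prohibits during the study, also lists topical keratolytics.
- **Open-label extension.** In its paragraph on the extension, Section 9.8.1 says: "If those standard of care treatments include prohibited medications, the subject should be discontinued from the study". No matching sentence covers Weeks 4 to 12 of the Double-blind Period.
- **Endpoints on that skin.** Section 13.1.4.1 makes the palm/sole score (through Week 12) and palm/sole fissures (at Week 12) secondary endpoints. Section 13.1.4.5 adds the proportion with a 2-grade palm/sole change at Week 12.
- **Analysis.** The primary efficacy population is ITT, analysed by assigned treatment (Sections 13.1.1 and 13.1.4). Section 13.1.4.3 says "change from Baseline in continuous secondary endpoints through Week 12 will be presented and analyzed using a mixed model for repeated measures", with treatment, subject and baseline score in the model. Section 13.1.4.5 uses logistic regression on treatment and age group for the 2-grade response, and multiple imputation for missing IGA outcomes.
- **IGA area.** Section 10.3.1.1 scores the IGA "excluding the following areas: knees, elbows, neck, palms, soles, axillae, groin, and scalp"; the face is not on that list. Section 9.8, after letting subjects continue usual care of face, scalp, hands and feet during washout, says: "The IGA will be evaluated on the rest of the body at Baseline".

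**The concern.** Starting standard of care is a post-randomization event triggered by how the skin is doing. If it is used more on vehicle, it hides a real effect of the cream on palms and soles. If it is used more on an active concentration, for instance because that cream irritates, it creates an apparent effect. In both cases the comparison is of cream plus differing amounts of keratolytic or urea, reported as a comparison of creams.

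The conflict between Sections 9.8.1 and 9.8.2 adds to this. It leaves open whether a subject using a keratolytic on the palms in Week 6 is within the protocol or has deviated from it, and so whether that subject belongs in the per-protocol population.

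**Working it through.** The protocol gives no figure for this point, so the check is mainly one of overlap, followed by an illustration with assumed inputs.

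**1. Timing.** Table 2-1 schedules palm/sole and fissure assessments after Baseline at Days 14, 30, 60 and 90 (Weeks 2, 4, 8 and 12). Standard of care is allowed after the Week 4 assessment. Two of the four post-Baseline readings, Weeks 8 and 12, can therefore be taken under it. The fissure endpoint and the 2-grade response use Week 12 alone, so each rests entirely on an exposed visit.

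**2. What the stated analyses do with such a reading.**
- Palm/sole score: the MMRM takes change from Baseline through Week 12. A score under standard of care is observed, and no term or rule sets it apart.
- 2-grade palm/sole response: the Week 12 score is classified as it stands.
- Fissures: the Week 12 difference in proportions uses the recorded status. Section 13.1.4.3 summarises number and pain descriptively and names no model for presence, so it is the estimated difference that is exposed.
- Multiple imputation replaces missing IGA outcomes only, so it does not touch any of these readings.
- Per-protocol: this set drops significant protocol deviations. Under Section 9.8.1 the use is permitted; under Section 9.8.2 it is prohibited. Whether the set removes these subjects cannot be determined.

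**3. The trigger.** Use on palms/soles depends on worsening of the IGA there, but the IGA as defined in Section 10.3.1.1 does not score palms or soles. How often standard of care will start cannot be predicted from the documents.

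**4. Illustrative size.** All rates and gains here are assumptions. Let rA and rV be the proportions using standard of care on palms/soles in an active arm and on vehicle, and g the average gain per user.

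Shift in the active-minus-vehicle benefit = (rA − rV) × g

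| rA | rV | g | Shift |
|---|---|---|---|
| 10% | 20% | 1 grade | −0.10 grade (understates the cream) |
| 10% | 30% | 1 grade | −0.20 grade (understates the cream) |
| 20% | 10% | 1 grade | +0.10 grade (overstates the cream) |
| 10% | 20% | fissures cleared in half of users | (0.10 − 0.20) × 0.5 = −5 percentage points |

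Equal use with equal gain gives no shift in the mean difference. The 2-grade response is probably the least affected: if worsening is judged against Baseline, a rescued subject must recover that loss and then gain two further grades.

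**The case against.** The strongest counter-argument is that rules for post-rescue data commonly sit in the SAP, which is not at hand. Section 13.1 calls itself a summary, and an ITT comparison regardless of added treatment is a legitimate choice. This stands in part. The protocol never says that values are analysed as observed; that follows from its stated models and from imputation confined to missing IGA. A SAP rule could settle the analysis, but it would not remove the conflict between Sections 9.8.1 and 9.8.2.

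A reader might infer four stronger things that the documents do not support:

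- **Open access from Week 4.** Use requires worsening and investigator approval. The condition limits how many subjects are affected, but it also ties use to outcome.
- **A clean baseline undone later.** Table 9-1 sets a 2-week keratolytic washout, but Section 9.8 lets usual care of face, scalp, hands and feet continue during washout. Those sites were not clearly promised a treatment-free baseline.
- **A compromised primary endpoint.** The IGA excludes palms and soles, so standard of care can reach it only through the face, and Sections 9.8 and 10.3.1.1 do not agree on whether the face is scored. Success also needs clear or almost clear skin and a 2-grade change on a full-body scale, which treatment of the face alone is unlikely to produce.
- **The discontinuation sentence settles it.** That sentence stands in the open-label paragraph and is not stated for the Double-blind Period.

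It is also fair to object that counting a user without fissures at Week 12 as having them overrides an observation. That is a composite definition of failure and should be labelled as such, with the observed result beside it.

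**Conclusion.** The point holds for the palm/sole score, palm/sole fissures and the 2-grade palm/sole response. Followed as written, the plan mixes an outcome-triggered second active treatment into those comparisons, and Sections 9.8.1 and 9.8.2 contradict each other on keratolytics in Weeks 4 to 12. No view is taken here on which clinical rule should govern.

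The direction of bias is not determined and the size is unknown. The 0.10 to 0.20 grade and 5-point figures rest wholly on assumed rates and gains. For the primary IGA the documents support only a question about the face, not a finding of bias. The conclusion assumes that no SAP rule already governs readings after standard of care starts.

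**What to change.** 1. Reconcile Sections 9.8.1 and 9.8.2 on keratolytics and urea in Weeks 4 to 12, and state whether such use counts as a deviation for the per-protocol set.
2. For the 2-grade palm/sole response and Week 12 fissures, count a subject with standard of care documented on palms/soles before Week 12 as a non-responder (for fissures, as fissure present). Report the as-observed result as sensitivity.
3. In the palm/sole MMRM, set scores after the start of palm/sole standard of care to missing, or multiply impute them, with as-observed as sensitivity. Do not carry the last value forward; Amendment 1 itself moved the primary sensitivity analysis from LOCF to multiple imputation. Setting scores to missing assumes that later scores can be predicted from earlier ones and the model terms.
4. Record the body site and start date of standard of care in the eCRF. Section 9.8.1 requires documentation but does not mention site. Tabulate use by arm, site and start week.
5. For the primary IGA, reconcile Sections 9.8 and 10.3.1.1 on whether the face is scored. If it is, add a sensitivity analysis counting subjects with standard of care on the face as non-successes.

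The cost is protocol and SAP wording, one eCRF item, slightly less favourable response rates, fewer scores at Weeks 8 and 12 in the MMRM, and a little more analysis work. Items 2 to 5 leave clinical management unchanged.
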